12.2 SAMPLE SIZE

Sample size calculation is based on the comparison of the 2 groups over 24 months incorporating a longitudinal mixed effects model. The number of participants, N, in each of the 2 groups²² is calculated as follows: We assume that, in the NT-501 group, the response of change in EZ area is as follows:

$$Y_{ij} = \beta_{0 NT-501} + \beta_{1 NT-501}x_{ij} + \varepsilon_{ij}, \quad j = 1, \dots, n; i = 1, \dots, m$$

For the sham group the sham equation holds as follows:

$$Y_{ij} = \beta_{0 Sham} + \beta_{1 Sham}x_{ij} + \varepsilon_{ij}, \quad j = 1, \dots, n; i = 1, \dots, m$$

Both groups have the same number of participants (m), $x_{ij} = x_j$ represents the duration between the first and the jth visit in which case $\beta_{1 Sham}$ and $\beta_{1 NT-501}$ represents the rates of change in Y for Sham and NT-501, respectively, and each person is measured at the same time points, and each participant has n repeated observations of EZ area at baseline, 12, 16, 20 and 24 months (where months will be converted to years).

The number of participants, m, in each of the 2 groups²² is calculated as follows:

$$m = \frac{2(z_{\alpha} + z_{\beta})^2 \sigma^2 (1 - \rho)}{ns_x^2 d^2}$$

where $d = \beta_{1 Sham} - \beta_{1 NT-501}$ and s_x^2 is the within-subject variance of x_j .

Using the above equation with a Type 1 error rate of 0.05 (2-sided); $\sigma^2 = 0.0256$; $\rho = 0.6$; $s_x^2 = 0.47$ and $n = 5$ (baseline and 12, 16, 20 and 24 months) we have 80% power with a sample size of 50 participants per treatment group to detect a difference in rate of change 0.037 mm²/year in the EZ area in the NT-501 group versus the sham group. The sample size will be increased to 56 participants per treatment group (112 total participants) to provide adequate power in the analysis of the population evaluable for efficacy.

The statistical model will be a random intercept model as follows:

$$Y_{ij} = (\beta_0 + b_0) + \beta_1 * TRT + \beta_2 * TIME + \beta_3 * TRT * TIME + \varepsilon_{ij}$$

where Y_{ij} is the efficacy endpoint (EZ area) measurement for participant $i = 1, 2, \dots, n$ at time point $j = 1, \dots, K$. TRT is an indicator of the participant i 's treatment group (ie, TRT = 1 for NT-501; TRT = 0 for sham) and TIME is the annualized time. To compare the rate of change from baseline in EZ area between the 2 treatment groups the primary hypothesis is as follows:

$$H_0: \beta_3 = 0 \text{ versus } H_1: \beta_3 \neq 0$$

12.3 STATISTICAL METHODS

12.3.1 Primary Endpoint(s)

The primary hypothesis is that NT-501 will slow the rate of change in the EZ (IS/OS) area loss. The primary efficacy endpoint will be analyzed using the mITT population (main analysis) but restricted to only those participants with at least 3 visits recorded. Baseline, Month 24, and at least one of Month 12, 16, or 20. A similar analysis will also be conducted with the PP Population.

The primary efficacy variable will be the rate of change that will be determined by using values from the EZ area as measured by SD-OCT. EZ area will be defined as the mean of 2 independent readings of the single eligible SD-OCT enface image taken at baseline and Months 12, 16, 20, and 24. A longitudinal mixed model will include EZ area as the dependent variable, a random intercept term to account for within subject variability, treatment group, time as a continuous variable, and the interaction between treatment and time. Time will be captured as the relative study day (defined as days since date of surgery) of the respective efficacy assessment and will include the days corresponding to the Baseline, Month 12, 16, 20, and 24 visits. The difference in the rate of change in EZ area over 24 months (to be computed by including baseline and Months 12, 16, 20, and 24 EZ measurements) will be compared using a random intercept model and the corresponding 95% confidence interval (CI), SE, test statistic, and p-value of the difference between treatment group parameters by computing the parameter estimate for the treatment by time interaction term. An Unstructured covariance structure will be implemented as with continuous time there will be a single parameter each for between and within participant variability.

12.3.2 Secondary Endpoint(s)

The secondary endpoints will be analyzed using the mITT population and the PP population to test for superiority of NT-501 over sham. The secondary endpoints are listed below:

- Mean change in aggregate sensitivity of microperimetry within the EZ line break area through 24 months
- Mean change in reading speed from baseline through 24 months
- Mean change in the NEI-VFQ-25 near activities subscale score from baseline through 24 months

Continuous secondary outcomes will be analyzed using a longitudinal mixed effects model and the corresponding 95% CI, SE, test statistic, and p-value of the difference between treatment group means at the 24-month time point will be computed. For the mixed effects model, fixed effects will include the treatment group (between-participant factor) and the visit (within-participant factor). The unstructured covariance matrix is preferred for this analysis. If the model does not converge, the “best” covariance structure will be chosen based on Akaike’s Information Criteria²³.

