The safety population will include the data from all randomized participants who receive any treatment and have at least 1 safety measurement. Participants will be analyzed in the group according to the treatment received, and no subjects (or data) will be excluded from this dataset because of protocol violations that occur during the study.

The efficacy analysis will be conducted on the mITT population and on the PP population. Safety analyses will be performed using the safety population. The handling of participants with missed visits or visits occurring outside the specified windows will be considered in the SAP.

If both eyes of a participant qualify for the study, the study eye will be selected using the centralized randomization process.

Continuous variables will be summarized using descriptive statistics (n, mean, standard deviation [SD], median, minimum, and maximum), and categorical variables will be summarized using the count and percentage of participants in each category.

Significance Level:

A significance level, α , of 0.05 will be used for statistical testing of the primary and secondary endpoints.

A hierarchical testing procedure will be applied to secondary efficacy analyses to control the overall type I error rate. In the case that the primary efficacy analysis is statistically significant at a 2-sided type I error rate of 0.05, the secondary efficacy endpoints will be tested at a 2-sided type I error rate of 0.05 in the order listed below. If any of the secondary endpoints are found to be not statistically significant at the 2-sided 0.05 level, the hypothesis testing will stop. Later endpoint(s) after a non-statistically significant result will be summarized descriptively and p-values may be produced for descriptive purposes only.

- Mean change in aggregate sensitivity of microperimetry within the EZ line break area from the Baseline Visit through the Month 24 Visit
- Mean change in reading speed from the Baseline Visit through the Month 24 Visit
- Mean change in the National Eye Institute Visual Function Questionnaire-25 (NEI-VFQ-25) near activities subscale score from the Baseline Visit through the Month 24 Visit

Accounting for Missing Data:

Every attempt will be made to collect data per the protocol and to avoid missing data. As such, dropouts and missing data are expected to be minimal, but can inevitably occur. For cases with unavoidable missing data, no imputation will occur.

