12.3.3 Analysis of Safety

Safety analyses will be performed on all participants who underwent either implant surgery or the sham procedure. The assessment of safety will be based on the summary of ocular and nonocular treatment-emergent AEs (TEAEs) and ophthalmic examinations. The Medical Dictionary for Regulatory Activities (MedDRA) nomenclature will be used to code AEs.

The TEAEs will be presented by treatment group (NT-501 versus sham). Summaries for TEAEs include the following: all TEAEs regardless of causality, treatment-related TEAEs, ocular TEAEs, treatment-related ocular TEAEs, TEAEs by intensity, SAEs, and TEAEs leading to discontinuation from the study.

The number and proportion of participants with a loss in BCVA of 15 or more letters from baseline in the study eye will be tabulated and presented by treatment group.

Detailed methods for the analysis of all endpoints will be outlined in the SAP.

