9.2 Secondary Efficacy Analysis

The secondary endpoints will be analyzed using the mITT Population and the PP Population to test for superiority of NT-501 implant over sham. The secondary endpoints are listed below:

- Mean change in aggregate sensitivity of microperimetry within the EZ line break area from the Baseline Visit to the Month 24 Visit
- Mean change in reading speed from the Baseline Visit to the Month 24 Visit
- Mean change in the National Eye Institute Visual Function Questionnaire-25 (NEI-VFQ-25) near activities subscale score from the Baseline Visit to the Month 24 Visit

The observed change from Baseline visit to the Month-24 visit will be compared using t-tests. The analyses will be based on the actual values observed at the Baseline and the Month-24 visit efficacy assessment, regardless of timing of the visit as long as it occurs within +/- 30 days for pre-COVID period or within +119 days post-visit timepoint for COVID-related delays. The estimated mean treatment effect, a 95% confidence interval (CI), and a 2-sided p-value will be provided. No imputation of missing data will be done.

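### Protocol 12.3.2 asks for a Month 24 treatment difference from a model with no treatment-by-visit term, and the SAP states the same secondary tests in two other ways

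*Protocol*

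**What the plan says.** Protocol 12.3.2 analyses the three secondary efficacy endpoints (aggregate microperimetry sensitivity, reading speed, NEI-VFQ-25 near activities) with a longitudinal mixed model. The target is explicit: the "difference between treatment group means at the 24-month time point will be computed". The model is described as follows: "fixed effects will include the treatment group (between-participant factor) and the visit (within-participant factor". No treatment-by-visit term is listed. On covariance: "The unstructured covariance matrix is preferred for this analysis".

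The primary model in Protocol 12.3.1 does name its interaction: "treatment group, time as a continuous variable, and the interaction between treatment and time". Protocol 12.2 writes the same term out as the tested coefficient.

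Under Protocol 12.1, once the primary succeeds, "the secondary efficacy endpoints will be tested at a 2-sided type I error rate of 0.05 in the order listed below", and testing stops at the first non-significant result. Microperimetry comes first.

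Protocol 12.3.3 defers detail: "Detailed methods for the analysis of all endpoints will be outlined in the SAP". The SAP then gives two answers. Section 9.2 says: "The observed change from Baseline visit to the Month-24 visit will be compared using t-tests". Appendix B assigns MMRM to the same three endpoints and lists no fixed effects. SAP section 12 records no change to the planned analyses.

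**The concern.** A model with main effects for treatment and visit has a single treatment parameter. Its fitted treatment difference is the same at every visit, so reading it off at Month 24 does not make it a Month 24 quantity. It equals the Month 24 difference only if the effect does not change over time.

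What is at stake is the meaning of the reported secondary result and, if the effect builds up, the chance of passing the hierarchy. Microperimetry has the most early visits and stands first, so a loss there would also block reading speed and NEI-VFQ-25. A programmer who builds Appendix B's MMRM has only Protocol 12.3.2 to take the fixed effects from.

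**Working it through.** **The plan's own figure.** The documents give no sample size or power for the secondary endpoints. The primary calculation reproduces: 2 × (1.960 + 0.842)² × 0.0256 × 0.4 / (5 × 0.47 × 0.037²) = 49.97, so 50 per arm. It does not bear on this point.

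**Inputs from the documents.** Two-sided 0.05; 56 per arm. Post-baseline microperimetry is at Months 6, 12, 16, 20 and 24 (Protocol 7.2.7 to 7.2.11). Reading speed and NEI-VFQ-25 are at Months 12 and 24 in the Protocol 7.2 visit lists and in SAP Appendix A, but the Protocol's Schedule of Events also marks Months 16 and 20. Both versions are computed.

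**Assumptions, because the documents are silent.** The response is change from baseline. The true difference grows linearly from zero at baseline to its full size at Month 24. Change scores have equal variance and a common correlation r of 0.3 to 0.8. Data are complete.

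**Step 1: what the model estimates.** With change-score covariance S and true visit differences d, the common treatment effect is w'd, where w = S⁻¹1 / (1'S⁻¹1). With K visits and common correlation, every weight is 1/K.

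**Step 2: power.** The standardised effect relative to a Month 24 test is R = share / √[(1 + (K − 1)r)/K]. Where the Month 24 test has 80% power, power becomes Φ(2.802R − 1.960). Example, microperimetry at r = 0.5: R = 0.65/√0.60 = 0.839, and Φ(0.391) = 65%.

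| Endpoint and visits (months) | Share of Month 24 difference | Power, r = 0.3 | r = 0.5 | r = 0.8 |
|---|---|---|---|---|
| Microperimetry: 6, 12, 16, 20, 24 | 78/(5 × 24) = 65% | 78% | 65% | 51% |
| Reading speed, NEI-VFQ-25: 12, 24 | 36/(2 × 24) = 75% | 74% | 68% | 60% |
| Reading speed, NEI-VFQ-25: 12, 16, 20, 24 | 72/(4 × 24) = 75% | 86% | 76% | 63% |

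For scale, a true 13.5 words per minute at Month 24 (the Phase 2 reading-speed difference) would be reported as 0.75 × 13.5 = 10.1.

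**Step 3: unequal weights.** An unstructured covariance need not weight visits equally. Suppose variance grows with time: S = tt' + I + J in residual-variance units, with t = month/24. For Months 12 and 24, S = [[2.25, 1.5], [1.5, 3]], so w = (2/3, 1/3) and the share is 2/3 × 0.5 + 1/3 = 67%, with power 63%. The same calculation for microperimetry gives 49% and 48%.

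**Step 4: other effect shapes.** A constant effect gives a share of 100%. An effect at half size at Month 6 and full from Month 12 gives microperimetry (0.5 + 4)/5 = 90%.

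**Step 5: simulation.** 4,000 trials, 56 per arm, r = 0.6, unstructured covariance estimated, linear effect. Without the interaction the estimates averaged 65% (microperimetry) and 75% (Months 12 and 24) of the truth, with power 60% and 63%. The Month 24 contrast recovered 99% to 100%, with power 79%.

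**The case against.** The strongest reply is that SAP 9.2 governs. The Protocol leaves detailed methods to the SAP, and the t-tests there use only Baseline and Month 24, so they average nothing. This stands. A reader might infer from Protocol 12.3.2 that the secondary tests will be biased toward zero; the documents do not support that, because the bias arises only if the protocol model is run literally or Appendix B's MMRM is built on the same two terms.

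SAP 9.2 does not close the matter, though. Appendix B of the same SAP contradicts it, and section 12 does not declare the t-test as replacing the protocol model. Nor can the SAP simply be taken as the later word: its section 4.1 still has Month 36 and 48 follow-up running to about August 2022, which Protocol 4.1 ends, and its preface names NTMT03-A where this protocol is NTMT-03-B.

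Second, the list of fixed effects may not be exhaustive, and asking for a 24-month difference suggests an interaction was meant. That is a fair reading, but the primary model spells its interaction out, so the omission should not be left to interpretation.

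Third, a reader might take a growing effect as established, since MacTel is progressive. The documents give no secondary-endpoint difference before Month 24. The later Phase 2 reading-speed differences shrink: 13.5, 10.6 and 5.4 words per minute at Months 24, 36 and 48. Linear growth is an assumption; an effect that peaked before Month 24 would be overstated by the averaging, not understated.

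**Conclusion.** The point holds in two parts. Protocol 12.3.2 states a Month 24 target that its listed model does not estimate. And the hierarchical secondary test is given three ways (Protocol 12.3.2, SAP 9.2, SAP Appendix B) that do not agree.

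The size is conditional on the protocol model being fitted literally, on linear divergence and on the covariance. Equal weighting gives 65% of the Month 24 difference for microperimetry and 75% for the other two. With 80% power for a Month 24 contrast and r from 0.3 to 0.8, power is about 78% to 51% for microperimetry and 74% to 60% for the other two at Months 12 and 24 only. Adding Months 16 and 20 raises the latter to about 76% at r = 0.5, and at r = 0.3 to 86%, above the Month 24 test itself. A single figure for the loss would therefore be too precise.

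With no effect at any visit the main-effects test keeps its nominal type I error. The issue is a clear estimand and possible loss of power on secondary endpoints: should-fix, not must-fix.

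**What to change.** Before database lock and unmasking, name one primary method for the three secondary tests and state it identically in Protocol 12.3.2, SAP 9.2 and SAP Appendix B. Record the choice in SAP section 12.

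- If it is the mixed model: response is change from baseline; fixed effects are treatment, categorical visit and treatment-by-visit; the test is the treatment contrast at Month 24. List the visits that enter for each endpoint.
- If it is the t-test: remove the mixed model from Protocol 12.3.2 and MMRM from Appendix B, or label it as a sensitivity analysis with the interaction included.

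With complete data the two give the same Month 24 estimate. They differ in how they use participants with missing visits, which is why the choice should precede unmasking. Adding an interaction to 12.3.2 alone would leave the conflict with SAP 9.2 in place.

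Reconcile the Month 16 and 20 entries for reading speed and NEI-VFQ-25 between the Protocol's Schedule of Events, the Protocol 7.2 visit lists and SAP Appendix A. The cost is a few lines of wording in both documents and no new data.

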12.3.3 Analysis of Safety

Safety analyses will be performed on all participants who underwent either implant surgery or the sham procedure. The assessment of safety will be based on the summary of ocular and nonocular treatment-emergent AEs (TEAEs) and ophthalmic examinations. The Medical Dictionary for Regulatory Activities (MedDRA) nomenclature will be used to code AEs.

The TEAEs will be presented by treatment group (NT-501 versus sham). Summaries for TEAEs include the following: all TEAEs regardless of causality, treatment-related TEAEs, ocular TEAEs, treatment-related ocular TEAEs, TEAEs by intensity, SAEs, and TEAEs leading to discontinuation from the study.

The number and proportion of participants with a loss in BCVA of 15 or more letters from baseline in the study eye will be tabulated and presented by treatment group.

Detailed methods for the analysis of all endpoints will be outlined in the SAP.

12.3.4 Demographic and Baseline Characteristics

Participant demographic and baseline characteristics will be summarized for the ITT analysis population. The comparability of groups used in comparison analyses will be characterized in tables of demographic data. Summary tables will be supported with individual participant data listings.

12.4 INTERIM ANALYSIS

No interim analysis for efficacy is planned for this study.

Prior to the completion of the study and database lock, summaries of the distribution of timing of efficacy visits (excluding any efficacy variables themselves) will be compared between treatment arms to determine if the pattern of visit attendance is comparable between treatment arms.

In addition, masked summaries of the overall results will be analyzed to determine appropriate parameterization of time as a continuous or categorical variable for the primary efficacy analysis. The determination of non-linearity will be concluded if the observed pattern of EZ area loss response over time follows a distinctly non-linear trend. Assessment will be made through an overall linear regression goodness-of-fit analysis, including review of a residual plot from a simple linear regression.

The analysis will be limited in scope and will not reveal unmasked results. No type I error adjustment will be made.

13. STUDY RISKS

Studies of intravitreal CNTF delivered by ECT have been performed in human participants with RP, atrophic AMD, and MacTel. A total of 180 human participants have been exposed to the 20 ng/day dose in randomized clinical studies. This is the same dose that will be tested in the proposed Phase 3 trial. A further 59 participants were exposed to a lower dose and in this group, miosis and change in dark adaptation were not reported.

Miosis: In the controlled clinical studies of AMD, RP, and MacTel (Phase 1 and Phase 2 studies), 40 of 180 (22.2%) participants reported miosis as an AE. These events were reported by participants. The prevalence of these findings was confirmed by the DSMC in their review of the data. The DSMC in their review of these data confirmed that the potential benefit outweighed the risk of this event.

The intracellular mechanisms through which the trophic factor CNTF regulates cholinergic development were examined in sympathetic neuron cultures²⁴. Treatment with CNTF increased levels of choline acetyltransferase activity significantly, thus confirming the parasympathetic agonist effect of CNTF. Stimulation of the parasympathetic nervous system (PSNS) results in constriction of the pupillary muscles. Constriction of the

pupil occurs when the circular muscle, controlled by the PSNS, contracts. This is the most likely mechanism for CNTF causing miosis. At lower doses in the Phase 2 studies of RP, this effect was not observed.

In addition, in the Phase 2 study of MacTel, pupil size was measured routinely throughout the duration of the study in all participants. The majority of eyes that received the implant had a reduction in the size of the pupil of approximately 1 mm. This effect was not seen in sham eyes but was present in over 90% of all treated eyes. The reason that only approximately 20% of the participants complained about the miosis is possibly related to the lack of any clinical symptoms and of noticeable effect for the participants. Certainly, no participant asked to have the device removed as a result of noting this well-described drug effect.

Delayed Dark Adaptation: This AE has only been reported in study participants with MacTel with 11 cases out of the 55 (22%) implanted eyes in the Phase 1 and 2 studies. In the studies of participants with RP and atrophic AMD, this AE was not reported. The cause of the delayed dark adaptation is not well understood, but a plausible explanation is that it is related to either miosis and/or the observed effect on photoreceptors following treatment with CNTF¹⁰. CNTF treatment results in a change in rod photoreceptor nucleus phenotype, featuring an increase in euchromatin and an increase in nuclear size. Chronic stimulation of retinal cells with CNTF has been shown to affect gene expression in photoreceptors including reduction of phototransduction genes such as rhodopsin in animal models²⁵. As rod photoreceptors are more light sensitive than cone cells and are almost entirely responsible for night vision, it is possible that the CNTF-mediated changes in the rod photoreceptors may affect the participant's ability to adapt to the dark. The reason why this AE is limited to a small subpopulation of the participants with MacTel is not well understood.

An increase in retinal thickness is observed in the majority of all eyes treated with CNTF at the dose proposed for study in Phase 3. Taken together, the preclinical data in dogs and the fact that macular thickening is seen only in the treated eyes, suggest that the AE of delayed dark adaptation may well be a direct consequence of CNTF treatment.

There are risks associated with the diagnostic procedures required for participants in this study. However, these are standard procedures that are performed as part of a normal eye and medical examination. Some of the discomforts associated with the ocular examination include the following:

- Dilating drops or anesthetic drops may sting. They can cause an allergic reaction, or if contaminated, can cause an infection, but neither of these problems is very likely to occur.
- Dilating drops can also cause a sudden increase of pressure (acute glaucoma) in eyes that are already predisposed to develop this condition. There is little risk of glaucoma being triggered in this way, but if it is, treatment is available.
- In rare instances, the cornea may be abraded during measurement of IOP or the use of a contact lens (used for examination purpose only and not a contact lens used to correct a participant's refractive error).

There are risks associated with the procedures required for participants in this study. The fluorescein angiogram requires injection of dye in the participant's arm. Local subcutaneous infiltration of dye may create discomfort and temporary staining of the skin (< 5% risk). There is a chance of fainting, ecchymosis at the site of injection, and a remote possibility of cellulitis from the needle track. After the dye injection, some participants (< 5%) may experience nausea that usually passes after a few seconds, and rarely, participants vomit.

Allergic reactions to fluorescein are uncommon; reactions may cause hives and itching. These reactions are usually treated with oral or injectable antihistamines as needed. Anaphylaxis from fluorescein is extremely rare and may be life-threatening. Fluorescein dye routinely causes a yellowing/orange color to the skin and urine that generally passes in 24 hours.

Imaging using OCT is an FDA-approved technique, which is not associated with any AEs.

Fundus photography and autofluorescence are not associated with any AEs, although some participants may experience mild discomfort due to the bright lights.

There are also risks associated with the operations to implant and explant the device and with the sham procedure. In general, the risks of intraocular surgery are very small. Some side effects could occur locally in the eye and could affect the participant's vision. There may be pain or infection, a small amount of bleeding, miosis, retinal detachment, cataract, vitritis, and/or mild astigmatism. In many cases, topical antibiotics and topical steroids can treat minor degrees of inflammation or infection. More serious infection or inflammation may require further surgery on the eye, likely with removal of the implant. The sham procedure of subconjunctival injection of lidocaine and inserting a final suture in the conjunctiva may be accompanied by subconjunctival bleeding, pain, or infection, all of which can be readily treated without any functional changes or any other permanent structural changes.

The risks of the sham procedure include: the risk of pre-operative sedation, the risk of the local anesthetic, and the risk of the superficial conjunctival incision and suture.

A possible complication of the explant surgery to remove the NT-501 device is retinal detachment. The probability of retinal detachment in the normal population is less than 1%. These other side effects are also possible (each with a probability of less than 1%):

- Bleeding in the eye
- Cataract
- Infection
- Inflammation inside the eye

Surgery to remove the NT-501 device may result in pain, loss of vision, or blindness in rare cases. Some of these side effects can be treated with medication either by mouth or injections in or around the eye. Some side effects may require treatment with a laser or surgery on the eye. A small sample (about 0.1 mL) of the vitreous along with the device may be collected and shipped back to the sponsor for analysis.

